7.3 Clinical Response Evaluation

The clinical evaluation will include an evaluation of CDI recurrence to assess clinical response on each follow-up contact for 60 days after FMT.

If subjects experience diarrhea (3 or more watery stools/day for two consecutive days) and suspect CDI recurrence, they should inform the study team and be recommended to contact their physician to perform a stool test for *C. difficile*. EPDL will test scheduled stool specimens and any unscheduled illness stool submitted up to days 60-70 after treatment for *C. difficile* toxins A/B in weekly batches but this should not delay treatment. If the test is positive, they should be treated by their physician. The Principal Investigator will be available for consultation with the attending physician. A form letter may be faxed or emailed to subject's physician about CDI recurrence.

Subjects requiring a systemic Non- *C. difficile* antibiotic within 60 days following FMT treatment will be excluded from the study for efficacy analysis, but will be followed for safety. Exclusion from efficacy means subjects will no longer provide stool specimens. However, subjects will continue to have phone visits and submit diaries till 180-200 days (the end of the study) for safety assessment (AEs). Subjects requiring a systemic Non- *C. difficile* antibiotic 60 days after FMT treatment will continue to be followed for efficacy and safety.

Subjects will be recommended not to use non-dietary probiotics and bile-acid sequestrants within 60 days after FMT treatment; however, subjects who take probiotics and bile-acid sequestrants within 60 days after treatment will not be excluded and continue

7.4 Patient Laboratory Evaluations – Fecal Sample

Stool samples will be collected by the subject and brought to the EPDL within 6 hours of collection if possible or as quickly as possible (if not feasible stool samples may be shipped via Federal Express) before FMT and at follow up days 1(+3), 7(+3), 14(+3), 30(+10), 60(+10), 90(+10) and any unscheduled visit up to 60-70 days after FMT treatment (excluding weekends and holidays). Stool samples collected from subjects until 60-70 days post FMT or unscheduled visit will be tested for *C. difficile* toxins A/B at EPDL in weekly batches. All the stool samples will be stored at -80°C for future metagenomics/microbiome analysis.

The University of Texas Health Science Center at Houston Enteric Pathogens Diagnostic Laboratory may conduct future biochemical research on specimens routinely and specifically collected during this clinical study that may be used for future research and may be stored for up to 15 years.

7.5 Health Outcome Assessment

Information such as mortality from any cause and hospitalizations will be collected through AE assessments. Subjects will report their solicited and unsolicited adverse events to study personnel on follow-up phone visits.

7.6 Subjective FMT Experience Assessment

On Treatment Day 1 in clinic, study personnel will inquire from subject if experienced any objectionable taste or smell or difficulty swallowing the capsules and general reaction on taking PRIM-DJ2727 capsules. The diaries on follow up days 7 and 180 will include a brief survey to assess subject-reported experience of FMT treatment.

8. STUDY SCHEDULE

8.1 Enrollment (Day -14 to -1)

The following study activities/data will be collected at the enrollment visit:

- After full explanation of the study protocol, have each subject sign an Informed Consent Form (ICF) before performance of any study-related procedures (including screening procedures).
- Assess each subject to ensure all inclusion criteria are met and no exclusion criteria met.
- Obtain standard demographics (date of birth, gender, ethnicity, race)

- Obtain medical history to record baseline conditions, current medications and CDI history (test result, treatment, hospitalization, weight and if any antibiotics used prior to first CDI episode). History will include obtaining information on solicited symptoms such as diarrhea, nausea, vomiting, gas/flatulence, abdominal distension, abdominal cramps/pain, constipation, rectal bleeding, fatigue/malaise, chills/shivering, and fever (>99.9 F) for two-week prior to enrollment to determine baseline patterns should an adverse event occur in the future.
- Instruct patients that should they enroll in the study, they will need to meet the following requirements:
 - Sexually active male and female subjects of childbearing potential must use an effective contraceptive method of birth control throughout the study which may include any of the following; abstinence, barrier methods (such as a condom or diaphragm) used with a spermicide, approved hormonal contraceptives (such as birth control pills, patches, implants or injections), intrauterine device (IUD), or surgical sterilization (such as tubal ligation, hysterectomy, or vasectomy) at any time in the past. Post-menopausal women ≥ 45 years of age must be amenorrheic for at least six months to be considered to not have childbearing potential.
 - Probiotics and bile-acid sequestrants should be stopped 24-96 hours before the FMT treatment.
 - On 24-96 hours before FMT, subjects take their last dose of antibiotic treatment for their CDI, non-dietary probiotics and bile-acid sequestrants. Any other antibiotics being taken must complete 14 days prior to FMT treatment.
 - On Day -1, all subjects must follow a clear liquid diet the entire day. In the evening around 6:00pm, subjects (treatment groups 1-3) must take bowel preparation i.e. 1 bottle (10 oz.) of magnesium citrate or patients with impaired kidney function take 250mL of GoLytely. GoLytely will be prescribed by the investigator or nurse practitioner. If bowel prep is missed, subject can still proceed with FMT (noted as protocol deviation).

- On Day 1, subjects (treatment groups 1-3) will take 4mg (2 capsules) of loperamide (Imodium) the morning of treatment (if Imodium is missed, can be taken within 12 hours after FMT treatment).
- On Day 1, subjects take first dose of oral capsules of PRIM-DJ2727 and recommended to continue their clear liquid diet for 1 hour after dosing.
- Stool samples will be collected by the subject before FMT and at follow up days 1, 7, 14, 30, 60, 90 and any unscheduled visit up to 60-70 days after FMT treatment and brought to the EPDL within 6 hours of collection if possible or as quickly as possible (excluding weekends and holidays). Subject can collect pre-treatment stool on any day after enrollment and before bowel prep on Day -1, and can bring stool sample on treatment day 1 clinic visit. If a subject is unable to bring the sample to the EPDL (e.g. out of town), it may be shipped by Federal Express as expeditiously as possible. A FedEx shipping label, ice pack, Styrofoam container with shipping box and instructions will be provided to subjects to ship stool sample if they are not able to hand deliver to the EPDL. The EPDL will be closed on weekends and holidays. If the follow-up day falls on Friday, Saturday or Sunday, subjects can ship the sample on Thursday or the following Monday.
- Subjects should inform the study team if they experience diarrhea (passage of ≥ 3 watery stools per 24-hour period for two consecutive days) suspecting CDI recurrence and contact their physician to perform a stool test for *C. difficile*. The EPDL will test scheduled stool specimens and any unscheduled illness stool submitted up to 60-70 days after treatment for *C. difficile* toxins A/B in weekly batches but this should not delay treatment. If the test is positive, they should be treated by their physician. The Principal Investigator will be available for consultation with the attending physician. A form letter may be faxed or emailed to subject's physician about CDI recurrence.

- Subjects will need to complete and submit diaries before FMT and on follow up days 7, 14, 30, 60, 90 and 180 days after FMT treatment. Subject can deliver diaries with stool sample, or may be fax, email, or mail to the study site. For diary copies received in email or fax, an attempt will be made to obtain the originals from subjects to be taken to the study site subsequently. Diaries serve as a tool for the subject to record daily bowel movements and weekly weight. Subjects will be recommended to measure weight at home each Sunday morning before eating and record on follow up diaries, providing they have a scale or balance. If they do not have the means to measure their weight this is not a protocol deviation. Additionally, the pre-treatment diary will include daily record of solicited symptoms from enrollment until a day before treatment Day 1 to determine baseline patterns. Solicited symptoms include nausea, vomiting, gas/flatulence, abdominal distension, abdominal cramps/pain, constipation, rectal bleeding, fatigue/malaise, chills/shivering and fever (>99.9 F) The diaries on follow up days 7 and 180 after treatment will include a brief survey to assess subject-reported experience of FMT treatment.
- Subjects will receive phone call from study personnel at follow up visit days 1, 7, 14, 30, 60, 90 and 180 days after FMT treatment (within windows specified in Table 1) Subjects will be assessed for any adverse events, new illness symptoms, worsening of baseline illnesses including adverse events of special interest (new or worsening autoimmune conditions, and metabolic syndrome) and change in medication. Subject-reported weight data from diaries will be assessed for AE at days 60 and 180 phone visits. Subjects will be assessed for CDI recurrence and solicited symptoms (diarrhea, nausea, vomiting, gas/flatulence, abdominal distension, abdominal cramps/pain, constipation, rectal bleeding, fatigue/malaise, chills/shivering and fever (> 99.9 F) for up to 60 days after treatment. Subjects will be reminded to submit completed diaries and stool samples. Diary will not be

collected on follow up visit Day 1. Stool sample will not be collected on follow up visit day 180.

- Provide subject with stool collection kits at enrollment for collecting stool samples before treatment and at follow up days along with IRB approved pretreatment prep instructions, pre-treatment diary, stool collection instructions and directions to drop specimen.

8.2 Pretreatment Preparation (Day -4 to -1) Email or Phone Reminder

- Remind the subject of the clinic appointment time.
- Remind the subject not to take antibiotics or probiotics 24-96 hours before FMT treatment day 1.
- Remind the subject to maintain a clear liquid diet on Day -1.
- Remind all subject to collect a stool sample (if not submitted), for subject groups 1-3, this should be before beginning the Magnesium Citrate or GoLytely bowel preparation.
- Remind the subject (treatment groups 1-3) to consume a 10 oz. bottle of Magnesium Citrate or 250ml of GoLytely bowel preparation for subjects with impaired kidney function (investigator or nurse practitioner will call in a prescription if needed) on evening (around 6:00pm) before the FMT treatment Day 1 clinic visit.
- Remind the subject to take 4mg (2 capsules) of loperamide (Imodium) for study groups 1-3 on the morning of the first day (Day 1) of the FMT treatment (can be taken within 12 hour after FMT treatment if dose missed before).
- Remind the subject to continue taking routine prescription medications.
- Remind the subject to complete and bring the pretreatment diary card to the clinic visit.

8.3 FMT Treatment (Day 1)

Subjects will arrive at the clinic on Treatment Day 1.

8.3.1 Before Administering PRIM-DJ2727

- Medication containers (Day 1 and Day 2) of PRIM-DJ2727 will be taken from the EPDL to the clinic by study personnel.
- Obtain pretreatment stool sample from patient's at-home collection and deliver to EPDL if stool sample has not been delivered to EPDL prior to Day 1 Treatment clinic visit.
- Obtain and review the pretreatment diary card with subject to determine baseline pattern of solicited symptoms.

- Ensure subject (treatment groups 1-3) consumed a 10 oz. bottle of magnesium citrate or 250mL of GoLytely on Day -1. If bowel prep is missed, subject can still proceed with FMT and will be recorded as protocol deviation.
- Ensure subject (treatment groups 1-3) has taken 4mg (2 capsules) of loperamide (Imodium) that morning (can be taken within 12 hours after FMT if dose missed before).
- Confirm subject took their last doses of antibiotic treatment for the CDI 24-96 hours before, non-dietary probiotics and bile-acid sequestrants are not being taken, and any antibiotic for non-CDI treatment has not been taken in the last 14 days.
- If applicable, perform urine pregnancy test.
- Collect pre-treatment weight and vital signs (blood pressure, heart rate, respiration rate, oral temperature).

8.3.2 Administering PRIM-DJ2727

- Administer PRIM-DJ2727 capsules with water. Instruct subject that capsules are to be swallowed and not chewed. If subjects chew capsules, ask them to swallow and continue administering capsules.

8.3.3 After Administering PRIM-DJ2727

- Observe subject in the clinic for ≥ 60 minutes and assess for any adverse events.
- Ask subject if experienced any objectionable taste or smell or difficulty swallowing the capsules and general reaction on taking PRIM-DJ2727 capsules.
- Collect post-treatment vital signs (blood pressure, heart rate, respiration rate, oral temperature).
- Provide subject with container of PRIM-DJ2727 for Day 2 treatment
- Remind the subject to take Day 2 PRIM—DJ2727 capsules empty stomach next morning with water.
- Remind subject to continue taking routine prescription medications as needed, but antibiotics, non-dietary probiotics and bile-acid sequestrants may not be taken.
- Release subject with IRB approved aftercare instructions, paper diaries, visit scheduler, safe antibiotics list and specimen request form.

- 8.4 FMT Treatment (Day 2 Phone Visit)
- Ask subject to ensure PRIM-DJ2727 Day 2 capsules dose was taken.
 - Ask for any adverse events since Day 1 assessment.
 - Remind subject to follow the aftercare instructions provided on Day 1.
 - Remind subject to take routine prescription medications as needed, but antibiotics, non-dietary probiotics and bile-acid sequestrants may not be taken.
 - Remind subject to completely fill the diaries, and submit diaries and stools at follow-ups according to schedule and instructions provided by study team.
 - A form letter may be sent to subject's physician about FMT completion.
- 8.5 Phone Visit Follow-up Days 1(+3), 7(+3), 14(+3), 30(+10), 60(+10), 90(+10) and 180 (+20) after treatment
- Contact the subject by phone and/or email at follow up days 1, 7, 14, 30, 60, and 90 after treatment, within windows specified in Table 1 to:
 - Remind subject to collect stool sample that will be placed in a transportation container with ice pack and delivered to the EPDL within 6 hours of collection if possible or as quickly as possible (excluding weekends and holidays) to be stored in the EPDL at -80° degrees for possible future testing. Remind subject to put stool collection date on provided container (if already submitted, stool collection date should be confirmed). Stool sample will not be collected for follow up visit Day 180. If hand delivery is not possible, stool sample may be shipped by Federal Express as expeditiously as possible. A FedEx shipping label, ice pack, Styrofoam container with shipping box and instructions will be provided to the subject to ship stool samples if they are not able to hand deliver to the EPDL. The EPDL will be closed on weekends and holidays. If follow-up day falls on Friday, Saturday or Sunday, subjects can collect and ship the sample on Thursday or the following Monday.
 - Remind subject to bring completed diaries with the stool sample, or fax, or email, or mail to the study site. For diary copies received in email or fax, an attempt will be made to obtain the originals from subjects to be taken to the study site subsequently. Diary will not be collected on follow up visit day 1 after treatment.
 - Assess subject for any adverse events, new illness symptoms, worsening of baseline illnesses including adverse events of special interest (new or worsening autoimmune conditions, and metabolic syndrome) and change in medication. Assess and review subject-reported weight data from diaries for AE (>5% change from baseline weight) at days 60 and 180 phone visits.

- Assess subject for solicited symptoms such as diarrhea (passage of ≥ 3 watery stools per 24-hour period for two consecutive days), nausea, vomiting, gas/flatulence, abdominal distension, abdominal cramps/pain, constipation, rectal bleeding, fatigue/malaise, chills/shivering and fever (> 99.9 F) up to 60 days after treatment.
- If CDI recurrence is suspected, subjects should be recommended to contact their physician to perform a stool test for *C. difficile*. EPDL will test scheduled stool specimens and any unscheduled illness stool submitted up to 60-70 days after treatment for *C. difficile* toxins A/B in weekly batches but this should not delay treatment. If the test is positive, they should be treated by their physician. The Principal Investigator will be available for consultation with the attending physician. Subjects who are determined treatment failures by the investigator will not be followed further for clinical parameters. A form letter may be sent to subject's physician about CDI recurrence.

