INCLUSION CRITERIA	All subjects 1. Male and female subjects 18 years of age or older. 2. Sexually active male and female subjects of childbearing potential agree to use an effective method of birth control during the study. 3. Female subjects of childbearing potential must have a negative pregnancy test on the day of the procedure prior to administration of study drug. 4. Subject/LAR willing and able to provide informed consent. 5. Able to follow study procedures and follow-ups. 6. Subject must have an attending physician who will provide non-transplant care. 7. Medical history of ≥ 3 bouts of CDI in outpatient or ≥ 2 bouts of CDI in inpatient with either group having ≥ 2 positive fecal tests for C. difficile toxin and at least one bout of CDI within 6 months of enrollment. 8. Received at least two courses of standard-of-care antibiotic therapy for CDI. 9. Have a refrigerator at home to store the second dose of FMT overnight.

EXCLUSION CRITERIA	
 1. Unable to take capsules orally. 2. Requiring systemic non-C. difficile antibiotic therapy within 14 days prior to FMT. 3. Unwilling to stop taking non-dietary probiotics 24-96 hours prior to FMT. 4. Unable to stop taking bile acid sequestrants (e.g. cholestyramine) 24-96 hours prior to FMT. 5. Unable to stop use of drugs with CDI activity: oral vancomycin, oral or IV metronidazole, fidaxomicin, rifaximin or nitazoxanide 24-96 hours prior to FMT and after FMT. 6. Receipt of CDI monoclonal antibodies as treatment for the most recent bout of CDI. 7. Life expectancy of < 6 months. 8. In the opinion of investigator, subject for any reason, should be excluded from the study.
DURATION OF FOLLOWUP	The duration of study participation for each subject is up to 216 days including screening (14 days), treatment (2 days) and follow-up (180-200 days).
STUDY POPULATION	The target population are adults (≥ 18 years old) with ≥ 3 bouts of CDI in outpatients or ≥ 2 bouts of CDI in an inpatient with either group having ≥ 2 positive fecal tests for C. difficile toxin and at least one bout of CDI within 6 months of enrollment.
STUDY BLINDING	This is a double-blinded study for the groups randomized to receive pre-treatment bowel prep and Imodium.

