5.2 Dose of FMT Product

Subjects will receive varying doses of PRIM-DJ2727 on two consecutive days of FMT. The clinical team will receive medications for each subject in labeled (see CMC protocol for label details) standard opaque pharmacy-type plastic containers for Day 1 or Day 2. Because of adding placebo capsules to maintain consistent number of capsules per treatment, the clinical trial personnel and subjects will be blinded as to the drug dose allocation.

Subjects in group 1 will receive healthy microbiota collected from 50g stool for 2 consecutive days with bowel prep and Imodium. Subjects in group 2 will receive healthy microbiota collected from 100g stool on the 1st day of treatment and from 50g stool on the 2nd day of the treatment with bowel prep and Imodium. Subjects in group 3 will receive healthy microbiota collected from 100g stool for two consecutive days with bowel prep and Imodium. Subjects in unblinded group 4 will receive healthy microbiota collected from 100g stool for two consecutive days without bowel prep and Imodium.

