7.2 Clinical Evaluations

- At the time of Enrollment, patients will be evaluated for inclusion and exclusion criteria. Demographics and current medications will be documented. Medical history will be obtained with particular attention to the recent CDI history (test result, treatment, hospitalization, weight and if any antibiotics used prior to first CDI episode). History will include obtaining information on solicited symptoms such as diarrhea, nausea, vomiting, gas/flatulence, abdominal distension, abdominal cramps/pain, constipation, rectal bleeding, fatigue/malaise, chills/shivering and fever (> 99.9 F) for two-week period prior to enrollment to establish baseline patterns should an adverse event occur in the future.
- Subjects will collect fresh stool samples at home and bring to the EPDL in transportation provided containers with an ice pack within 6 hours of collection if possible or as quickly as

possible before FMT and at follow up days 1(+3), 7(+3), 14(+3), 30(+10), 60(+10) and 90(+10) and any unscheduled visit up to 60 days after FMT treatment (excluding weekends and holidays). Subject may collect pre-treatment stool on any day after enrollment and before bowel prep on day -1, and can bring stool sample on treatment Day 1 clinic visit. Stool samples collected from subjects until 60-70 days post FMT or at unscheduled visit up to 60-70 days will be tested for *C. difficile* toxins A/B at EPDL in weekly batches. All the stool samples will be stored at -80°C for future microbiome analysis. If a subject is unable to bring stool sample for any reason (e.g. out of town), subject will be asked to ship the sample by Federal Express as expeditiously as possible. A FedEx shipping label, ice pack, Styrofoam container with shipping box and instructions will be provided to the subject to ship stool samples if they are not able to hand deliver the stools to the EPDL. The EPDL will be closed on weekends and holidays. If the follow-up day falls on Friday, Saturday or Sunday, subjects can ship the sample on Thursday or the following Monday. Stool samples that are received out of window are not a protocol deviation; however, missed stool samples are a protocol deviation.

- Subjects will be assessed for vital signs (blood pressure, heart rate, respiration rate, oral temperature, weight) at the day 1 of treatment clinic visit.

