- Confirm that the C. difficile antibiotic was stopped 24-96 hours before the visit.
- Perform urine pregnancy test on all female subjects of childbearing potential prior to FMT administration.
- Weight and vital signs (blood pressure, heart rate, respiration rate, oral temperature) will be collected pre-treatment.
- Administer Day 1 dose and dispense Day 2 dose.
- Ask subject if experienced any objectionable taste or smell or difficulty swallowing the capsules and general reaction on taking PRIM-DJ2727 capsules.
- Observe the subject for 1 hour after dosing for any adverse events.
- Collect post-treatment vital signs (blood pressure, heart rate, respiration rate, oral temperature).
- Remind subject that Day 2 dose should be taken the next morning on empty stomach with water.
- Remind subject to continue taking routine prescription medications as needed, but antibiotics, non-dietary probiotics and bile-acid sequestrants may not be taken.
- Release subject with IRB approved aftercare instructions, follow-up paper diaries, visit scheduler, safe antibiotics list and specimen request form.

Second Treatment Dosage: Day 2 (Phone Visit)

- Ask that subject has taken the Day 2 dose.
- Ask for any adverse events since Day 1 assessment.
- Remind subject to follow the aftercare instructions provided on Day 1.
- Remind subject to continue taking routine prescription medications as needed, but antibiotics, probiotics and bile-acid sequestrants may not be taken.
- Remind subject to completely fill the diaries, and submit diaries and stools at follow-up visits according to schedule and instructions provided by study personnel.
- A form letter to subject's physician about FMT completion may be faxed or emailed.

Follow Up and Safety Assessment Period (Phone Visits): Post Treatment Days 1(+3), 7(+3), 14(+3), 30(+10), 60(+10), 90(+10) and 180(+20).

- Assess subject for any adverse events, new illness symptoms, worsening of baseline illnesses including adverse events of special interest (new or worsening autoimmune conditions and metabolic syndrome) and change in medication. Review and assess subject-reported weight data from diaries for AE (>5% change from baseline weight) at days 60 and 180 phone visits.

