- Assess subject for solicited symptoms such as diarrhea (passage of ≥ 3 watery stools per 24-hour period for two consecutive days), nausea, vomiting, gas/flatulence, abdominal distension, abdominal cramps/pain, constipation, rectal bleeding, fatigue/malaise, chills/shivering and fever (>99.9 F) for up to 60 days after treatment.
- If CDI recurrence is suspected, subjects should be recommended to contact their physician to perform a stool test for *C. difficile*. EPDL will test scheduled stool specimens and any unscheduled illness stool submitted up to days 60-70 after treatment for *C. difficile* toxins A/B in weekly batches but this should not delay treatment. If the test is positive, they should be treated by their physician. The Principal Investigator will be available for consultation with the attending physician. A form letter may be faxed or emailed to subject's physician about CDI recurrence.
- Subject will be reminded to submit completed diary (except on follow up visit Day 1) and stool sample (except on follow up visit Day 180) and to put stool collection date on provided container (if already submitted, stool collection date should be confirmed).
- Stool samples will be collected at home by the subject and dropped off at the EPDL in the University of Texas School of Public Health in transportation provided containers with ice pack within 6 hours of collection if possible or as quickly as possible (excluding weekends and holidays). Stool sample will not be collected for follow up visit Day 180. If the subject is unable to bring stool sample for any reason (e.g. out of town), subject will be asked to ship the sample by Federal Express as expeditiously as possible. A FedEx shipping label, ice pack, Styrofoam container with shipping box and instructions will be provided to the subject to ship stool sample if they are not able to hand deliver to the EPDL. The EPDL will be closed on weekends and holidays. If the follow-up day falls on Friday, Saturday or Sunday, subjects can ship the sample on Thursday or the following Monday. Stool samples that are received out of window are not a protocol deviation; however, missed stool samples are a protocol deviation.

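### The weekend rule lets the follow-up Day 1 stool move back to Thursday, which is a dosing day or the day before dosing and always ahead of the sampling window

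*Combined protocol and SAP*

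**What the plan says.** Section 8.5 gives the rule in its fullest form: for a follow-up day on Friday, Saturday or Sunday, "subjects can collect and ship the sample on Thursday or the following Monday". Section 7.2 (twice) and Section 8.1 give it for shipping only: "If the follow-up day falls on Friday, Saturday or Sunday, subjects can ship the sample on Thursday or the following Monday". In all four places it follows the text on courier delivery and laboratory closure. None of them exempts follow-up Day 1.

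The windows are one-sided. Section 7.2 and Table 1 allow +3 days at Days 1, 7 and 14 and +10 days at Days 30, 60 and 90, with nothing before the nominal day. Section 7.2 adds that stool received outside its window does not count as a deviation. Sections 7.2 and 8.5 have the subject write the collection date on the container, and staff confirm it if the sample has already been sent in.

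The product is given over two days (Section 5.2): "Subjects will receive varying doses of PRIM-DJ2727 on two consecutive days of FMT". The secondary endpoint (Synopsis, Sections 2 and 9.11) is improvement in microbiota diversity from baseline. The pre-treatment stool may be collected at any time from enrollment until the bowel preparation on Day -1 (Section 7.2).

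**The concern.** Because Thursday is set against the following Monday, it has to mean the Thursday before. A sample shipped on a Thursday was collected by that Thursday, so the shipping and collecting wordings lead to the same timing. Moving a sample backwards does not fit windows that only run forwards.

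At later visits this is a shift of a few days. At Day 1 the shift is as long as the gap between the visit and the doses, so the stool can land on a dosing day or before any product was taken. It would still carry the label of a post-treatment Day 1 sample. A stool taken on Day -1 would also fall in the period when the baseline sample may be collected, so the first change-from-baseline value could compare two pre-treatment stools. Whether this can happen depends on the weekday of dosing. The deviation log would not show it, and no section says how an early stool is assigned to a visit.

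**Working it through.** **1. Where follow-up days start.** The Synopsis and Section 7.1 give 14 days of screening, 2 of treatment and up to 200 of follow-up, for a maximum of 216 days. 14 + 2 + 200 = 216 reproduces the stated figure. Follow-up therefore comes after both treatment days, and follow-up Day 1 is the day after dose 2. The plan does not state this outright, so counting from dose 1 is shown as well.

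**2. Size of the shift.** From a Friday, Saturday or Sunday, the preceding Thursday is -1, -2 or -3 days and the following Monday is +3, +2 or +1 days. With windows of +3 or +10, Thursday is always before the window and Monday is always inside it.

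**3. Follow-up Day 1 moved to Thursday.**

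| Day 1 falls on | Counted from dose 2: Thursday is | Counted from dose 1: Thursday is |
|---|---|---|
| Friday | dose 2 day (doses Wed/Thu) | dose 1 day (doses Thu/Fri) |
| Saturday | dose 1 day (doses Thu/Fri) | Day -1 (doses Fri/Sat) |
| Sunday | Day -1 (doses Fri/Sat) | Day -2 (needs a Saturday clinic visit) |

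Under either count, the Thursday sample is never later than the last dosing day.

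**4. How many subjects are offered the option at Day 1.** The documents give no dosing weekdays. Assume first doses spread evenly over Monday to Friday.
- Counted from dose 2: Wednesday, Thursday and Friday starts trigger the rule, 3/5 = 60%.
- Counted from dose 1: Thursday and Friday starts, 2/5 = 40%.

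Within the 60%, a Wednesday start (1/5) puts Thursday on the dose 2 day. A Thursday start (1/5) puts it on the dose 1 day, before dose 2. Only a Friday start (1/5 = 20%) puts it before any product with certainty.

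**5. Later visits.**

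| Nominal day | Window | Possible Thursday day | Triggered, from dose 2 | Triggered, from dose 1 |
|---|---|---|---|---|
| 7 | 7-10 | 4-6 | 2/5 | 1/5 |
| 14 | 14-17 | 11-13 | 2/5 | 1/5 |
| 30 | 30-40 | 27-29 | 3/5 | 3/5 |
| 60 | 60-70 | 57-59 | 2/5 | 3/5 |
| 90 | 90-100 | 87-89 | 1/5 | 1/5 |

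The triggered shares use the same Monday-to-Friday assumption. The Thursday ranges cover all three trigger days.

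**The case against.** The rule is permissive, and the Monday alternative stays in window. Three of its four statements concern shipping and follow the courier fallback, so subjects who deliver by hand may seldom use it. The samples are defined as coming after treatment, which argues against reading the rule to allow one before any product. Under Section 8.5 the reminder call is made at the follow-up day within its forward window, and by then the Thursday before Day 1 has passed. Early samples can be identified from the recorded collection date. The plan also knowingly tolerates stool that arrives out of window.

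Much of this stands, and it limits the point:
- A reader might infer that 60% of Day 1 stools will be pre-dose. The documents do not support that. The 60% is the share offered a choice under an assumed dosing pattern, and nothing says how many would take it. Dose 2 is taken in the morning (Section 7.2), so a stool later on the dose 2 day follows both doses.
- A reader might infer that early samples cannot be detected. They can be. What is missing is a rule for using the recorded date.
- A reader might infer that the 60-day failure endpoint is compromised because a Thursday Day 60 stool is taken on Days 57-59. Those days lie inside the failure period. Failure also needs diarrhea and receipt of anti-*C. difficile* antibiotics, and illness stools are accepted for toxin testing up to Days 60-70.

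The objection does not remove the Day 1 defect. Subjects get the rule at enrollment (Section 8.1), and the Day 2 phone visit, when dose 2 is due, reminds them to submit stools on schedule. A subject can therefore act on the Thursday option before the Day 1 call. Tolerating late or early receipt does not make a mid-dosing stool a post-treatment one.

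**Conclusion.** The point holds as an inconsistency in sampling logistics that matters mainly at follow-up Day 1. As written, the rule can place a stool taken on a dosing day, or on Day -1, in the post-treatment Day 1 slot that feeds the diversity-from-baseline endpoint. This does not depend on whether days are counted from dose 2 or dose 1.

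The option is open to up to 60% of subjects at Day 1 counted from dose 2, or 40% counted from dose 1. Both figures assume first doses spread evenly over Monday to Friday, and actual use is unknown. The effect is smaller at Days 7 and 14, where the sample moves 1 to 3 days early. At Days 30, 60 and 90 it is negligible. Day 1 is one of six follow-up stools, and no section names it as the key diversity timepoint, so the secondary endpoint as a whole is not undermined. No material effect on the 60-day failure endpoint is shown.

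**What to change.** In Section 7.2 (both places), 8.1 and 8.5, delete *on Thursday or*, so that a Friday, Saturday or Sunday sample moves only to the following Monday. At minimum, state that the Thursday option does not apply to follow-up Day 1. Reconcile the shipping wording of Sections 7.2 and 8.1 with the collect-and-ship wording of Section 8.5. Add to Section 10.2 that each stool is assigned to a visit by its recorded collection date relative to the dose 1 and dose 2 dates, and that no stool taken before the end of dosing is analyzed as a post-treatment sample.

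The cost is a wording change in four places and in the subject instructions, plus one analysis rule that uses a date already collected. The one downside is a Monday holiday, which can push a Friday sample to Tuesday, +4 days. That is a day outside the +3 windows, but the plan already accepts out-of-window receipt, and the stool would still be after both doses.
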